6.2. Study Period

Visit schedules and study procedures will be different based on the line of treatment of the patients (ie, if enrolled from B1871006 vs. B1871008). Study visit can be performed with a ± 14 -day (2-week) window (1 month is defined as a 4-week or 28-day period).

- 1st line chronic phase patients enrolled from study B1871008 will be followed up only to collect safety, survival and BCR-ABL mutational status data (the latter does not apply to patients enrolled at China Sites). Study visits will occur every 12 months (once a year), and a phone call will be implemented every 3 months between study visits at the site in order to collect an update on the patient's current safety status and dosing and to remind the patient about use of the dosing diary and importance of contraception compliance. All information collected during the phone calls will be immediately recorded in the eCRF.

One additional study visit will be arranged after the first 3 months ± 4 days of treatment in order to collect all diarrhea information reported on the patient diarrhea card provided at the baseline visit.

Patients who are continuing bosutinib therapy should have their disease status assessed according to the local standard of care.

- For 2nd and later line patients enrolled from study B1871006, study visits will occur every 6 months (twice a year) and a phone call will be implemented every 3 months, between scheduled visits in order to get an update on current patient's status, assessment of any adverse events, and dosing compliance, and a contraceptive check.

Procedures performed as part of the study visits may include:

- Extramedullary disease assessment;
- According to standard of care and current treatment guidelines, bone marrow or blood sample will be collected for CML disease assessment via cytogenetic assessment by karyotype or by FISH. If appropriate, in lieu of cytogenetic assessment molecular response monitoring using reverse transcriptase polymerase

chain reaction (RT-PCR) for molecular assessment (of BCR-ABL fusion transcript levels in peripheral blood may be performed. These assessments will be performed at a laboratory local to Investigational Site and data will be collected if available.

- Hematology panel with complete blood counts (CBC) (see [Section 6.1](#) for details);
- Chemistry panel (see [Section 6.1](#) for details);
- Liver Function Tests (LFTs) (see [Section 6.1](#) for details);
- Bone Marrow Aspirate for differential ONLY for patients in advanced phase;
- Review of adverse events and concomitant medications.

One additional study visit will be arranged after the first 3 months on treatment in order to collect all diarrhea information reported on the patient diarrhea card provided at the baseline visit.

6.3. Treatment Completion Visit

The End of Treatment (EOT) visit should be performed for all patients once they have permanently discontinued bosutinib as described in [Section 5.3](#). The visit should occur within 28 days after the last dose of bosutinib. The following procedures are required:

- Complete physical examination including vital signs, ECOG performance status and extramedullary disease assessment;
- Electrocardiogram (ECG);
- Chest X-ray;
- Mutation analysis of the BCR-ABL1 transcript will be performed using a peripheral blood sample collected at the end-of-treatment visit in order to identify mutations acquired upon treatment with bosutinib. Mutations will be identified by direct sequencing of the BCR-ABL transcript performed at a Central Laboratory as arranged by the Sponsor. Peripheral blood for all eligible patients (except from patients enrolled at sites in China) will be collected and shipped frozen to a central vendor for analysis. Specific instructions for handling and shipment of these samples can be found in Study Reference Manual;
- Cytogenetic or residual molecular response testing. Molecular response monitoring using reverse transcriptase polymerase chain reaction (RT-PCR) measurement of BCR-ABL fusion transcript levels in peripheral blood may be performed in lieu of monitoring via cytogenetics, once molecular response is achieved, and according to standard of care and current treatment guidelines at investigative site;

- Hematology panel with complete blood counts (CBC) (see [Section 6.1](#) for details);
- Chemistry panel(see [Section 6.1](#) for details);
- Liver Function Tests (LFTs) (see [Section 6.1](#) for details);
- Coagulation tests (see [Section 6.1](#) for details);
- Dipstick urinalysis (microscopic if abnormal);
- Serum pregnancy test (for women of childbearing potential);
- Contraceptive check;
- Dosing compliance check;
- Review of adverse events and concomitant medications.

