2.2. Endpoints

The objective of the study is to provide long-term access to bosutinib treatment and assess long-term safety, tolerability and duration of clinical benefit, without any formal hypothesis testing; therefore, there is no formal primary endpoint.

In addition, data to be collected are planned to be different in the first line CP patients relative to the later line and advanced patients.

For all patients regardless of the line of treatment:

- Long-term safety of bosutinib, including type, incidence, severity, timing, seriousness and relatedness of AEs and laboratory abnormalities as well as reason of treatment discontinuation. A special focus will be made on diarrhea in order to satisfy the EMA post-commitment request;
- BCR -ABL mutations present at the time patients discontinue Bosutinib.
(For all patients except those enrolled at sites in China)
- Overall survival (OS);
- Fulfill the EMA post-approval requirement to compare the pharmacokinetic analysis of C_{trough} of bosutinib in this study to C_{trough} of previous studies.

For 2nd or later line patients coming from study who are still on treatment with **bosutinib**, the following efficacy endpoints will be assessed ([Appendix 1](#)):

- Duration of hematologic and cytogenetic responses;
- Progression free survival;
- Time to transformation to accelerated or blast phase.

Refer to [Section 7.1.1](#) for more details on endpoint definitions.

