5.6.1. Prohibited

All concomitant medications restrictions apply only **while the patient is on the active treatment phase of the study** (ie, receiving bosutinib), and include:

- Any anti-leukemia treatment other than the regimen defined in this protocol, including donor lymphocyte infusions;
- Any other investigational agents while the patient is receiving bosutinib.

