7.3.1. Blood Collections for Plasma PK and BCR-ABL Mutation Analysis

Blood samples (3 mL) to provide approximately 1.0 mL plasma for PK analysis will be collected into appropriately labeled tubes at times specified in the [Schedule Of Activities](#).

One pre dose PK sample per eligible patient will be drawn, to be collected at first occasion after at least 2 weeks of uninterrupted dosing at the same dose level. Actual date and time of treatment dose and PK sampling should be recorded on the eCRF.

Detailed instructions for PK blood sample collection, processing, storage, and shipment will be provided in a lab manual. PK samples must be processed and shipped as indicated in the lab manual to maintain sample integrity. Any deviations from the processing steps (ie, sample collection and processing, interim storage, or shipping conditions), including any actions taken, must be documented and reported to the Sponsor. On a case by case basis, the Sponsor may make a determination as to whether sample integrity has been compromised. Any deviation from the specified sample handling procedure resulting in compromised sample integrity will be considered a protocol deviation.

As part of understanding the PK of the study drug, samples may be used for further characterization and/or evaluation of the bioanalytical method. These data will be used for internal exploratory purposes and will not be included in the clinical report.

BCR-ABL Mutation Analysis

Analysis of the BCR-ABL transcript will be performed using a peripheral blood sample collected at the end-of-treatment visit from each eligible patient in order to identify mutations acquired upon treatment with bosutinib. Mutations will be identified by direct sequencing of the BCR-ABL transcript performed at a Central Laboratory as arranged by the Sponsor. Peripheral blood will be collected and shipped frozen to a central vendor for analysis. Specific instructions for handling and shipment of these samples can be found in Study Reference Manual.

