 - *For all lines of treatment, increasing WBC defined as doubling of WBC, occurring over a period of ≥ 1 month, with the second WBC $> 20 \times 10^9/L$ and confirmed at least 1 week later.*

For DOR and PFS, if there is an unacceptable gap between the date of progression or death and the date of the most recent prior disease assessment (>48 weeks), the event will not be used and censorship will be at the most recent prior assessment.

Transformation, defined by the first two progression bullets above, is the time from first dose to confirmed transformation ($[\text{date of transformation} - \text{first dose date} + 1]/7$). Confirmed transformation is defined as 2 consecutive assessments at least 1 week apart or 1 assessment confirmed by progression of disease or death. Patients without events are censored at the last hematologic or extramedullary assessment where transformation could be assessed.

BCR-ABL mutational status at treatment discontinuation will be assessed. Emergent mutations are defined as those mutations which were not present at baseline. B1871006 patients who were not assessed for baseline mutations are not assessable for emergent mutations. All B1871008 patients are assessable for emergent mutations.

OS is defined as the time from randomization for B1871008 patients and from first dose B1871006 patients to the date of death ($[\text{date of death} - \text{randomization/first dose date}]/30.4$). Patients who have not died will be censored at the last known alive date.

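### The BCR-ABL mutation sample may be drawn up to 28 days after the last dose and after the next therapy has started, and the SAP does not separate such samples, so the reported percentage may not describe status at discontinuation.

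*Protocol*

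**What the plan says.** Protocol 2.2 defines the endpoint as "BCR -ABL mutations present at the time patients discontinue Bosutinib", for all patients except those at sites in China. Protocol 6.3 and 7.3.1 and footnote q of both schedules in Table 1 provide one peripheral blood sample for it, at the end-of-treatment (EOT) visit, "in order to identify mutations acquired upon treatment with bosutinib". On the timing of that visit, Protocol 6.3 states: "The visit should occur within 28 days after the last dose of bosutinib".

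Protocol 5.6.1 bars "Any anti-leukemia treatment other than the regimen defined in this protocol", but limits the rule in time: "All concomitant medications restrictions apply only" during the active treatment phase, that is, while bosutinib is being taken.

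SAP 6.1 repeats the endpoint: "BCR-ABL mutational status at treatment discontinuation will be assessed". It defines an emergent mutation as one not present at baseline. SAP 8.2.1 reports the percentage of patients with such mutations.

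**The concern.** The endpoint is fixed at the moment bosutinib stops, and its purpose is to describe what was acquired on bosutinib. The sample can come four weeks later, and nothing requires it to precede the next tyrosine kinase inhibitor, chemotherapy or transplant. Once another drug is acting, the blood reflects both treatments.

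Two errors are then possible. A mutation that was present at discontinuation may have fallen below what direct sequencing detects. A mutation that arose after discontinuation would be counted as emergent, because the only comparison is with baseline. Patients who stop for progression or loss of response are the most informative about resistance and plausibly switch soonest, so the problem could be concentrated among them. That last step is an inference; the documents give no switch times.

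**Working it through.** The plan has no figure of its own to reproduce. There is no sample-size calculation (Protocol 9.1), no hypothesis (SAP 4.1) and no expected mutation frequency. The check sets the timing rules side by side.

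1. **Time of the endpoint.** Discontinuation of bosutinib (Protocol 2.2; SAP 6.1).
2. **Time of the sample.** Day 0 to day 28 after the last dose (Protocol 6.3). The schedule footnotes also give a general visit window of ±14 days. If that covers the EOT visit, the latest day is 28 + 14 = 42; the documents do not say whether it does.
3. **Overlap with new therapy.** The restriction in Protocol 5.6.1 ends when bosutinib ends, so new therapy is allowed on all 28 days. This is foreseen: Protocol 8.1.4 collects adverse events for at least 28 days after the last dose, and 8.1.4.2 says what to record if new anticancer therapy begins in that period.
4. **Patients stopped after a long interruption.** Protocol 5.3 lists interruption for more than 4 weeks (over 28 days) as a reason to discontinue. Protocol 6.3 holds the EOT visit once discontinuation is permanent, yet within 28 days of the last dose. If the decision comes only when the 4 weeks are exceeded, both cannot be met. These passages must be reconciled.
5. **Handling in the SAP.** SAP 6.1 and 8.2.1 contain no time limit, no flag for samples drawn after new therapy and no sensitivity analysis. SAP 6 ends the on-treatment efficacy window at treatment discontinuation for B1871006 patients, but does not say whether that window governs the mutation sample.
6. **Effect on the percentage.** Among sampled patients, let *s* be the share drawn after new therapy began. Among those, let *p* be the share with an emergent mutation detectable at discontinuation. Let *m* be the share of these in whom it is no longer found, and *a* the share of the remainder in whom a later mutation is found. Then

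   reported − target = *s* × [(1 − *p*) × *a* − *p* × *m*].

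   The error is zero when *s* = 0 and cannot exceed *s* in size. It is positive when (1 − *p*) × *a* exceeds *p* × *m*, and negative in the reverse case. The documents give none of *s*, *p*, *m* or *a*. If one mutation replaces another in the same patient, the percentage is unchanged but the listed mutation is wrong.
7. **Illustration for one sample (every input assumed).** New therapy starts on day 0, blood is drawn on day 28, and the mutant-to-unmutated ratio halves every 7 or 14 days. The odds f/(1 − f) are then divided by 2^(28/7) = 16 or 2^(28/14) = 4.
   - A 30% mutant share: odds 0.429, becoming 0.027 or 0.107, so 3% or 10%.
   - A 50% share: odds 1, becoming 0.0625 or 0.25, so 6% or 20%.
   - A 70% share: odds 2.333, becoming 0.146 or 0.583, so 13% or 37%.

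   If the next drug lowers both transcripts equally, the share does not move. If it spares the mutant so that the ratio doubles every 14 days, 30% becomes 0.429 × 4 = 1.714 in odds, or 63%.

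**The case against.** The 28 days are a maximum. Sampling on the day of the last dose is allowed, and nothing stops a site from drawing blood before a switch. The study is descriptive, with no primary endpoint, and no decision rests on this percentage. The affected group may also be small. Those treated in the extension were judged to be benefiting at entry (Protocol 3), and Protocol 1.2.2 reports for the first-line parent study that 24% of bosutinib patients stopped for adverse events and 7% for progression. Of the 37% who stopped, progression is therefore 7/37 = 19%. These points stand as limits on importance. They do not close the gap: nothing in the analysis distinguishes sites that drew early from those that did not, and patients who stop for toxicity may also start another drug.

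A reader might infer more, in four ways that the documents do not support.

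- **That the percentage is biased low.** This needs the next drug to suppress the mutant faster than the unmutated transcript, and it ignores later mutations counted as emergent. Step 6 shows that either sign is possible.
- **That most visible clones would be missed.** The falls in step 7 combine a switch on day 0, a draw on day 28 and a favourable decay rate. Even against an assumed detection limit of 20%, the slower rate leaves a 50% clone at the limit and a 70% clone visible.
- **That post-switch samples should be excluded.** If resistant patients switch fastest, exclusion would remove those most likely to carry mutations.
- **That the dates needed are already collected.** Protocol 6.4 collects details of subsequent therapy only if available and names no start date. Protocol 7.3.1 asks for date and time of dosing and of the PK sample, but states no such requirement for the mutation sample.

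**Conclusion.** The point holds. The plan permits samples that do not measure the stated endpoint, and the SAP cannot tell them from those that do. This rests on the text alone: an endpoint set at discontinuation, a single sample up to 28 days later, no restriction on new anti-leukemia therapy in between, and one percentage without a timing condition.

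The net direction and the size of the error cannot be computed from the documents. The error is limited to patients who began new therapy before the draw; those who did not are untouched by this mechanism. Because the endpoint is descriptive, this is an inexpensive improvement that should be made, and it does not threaten the study's other results.

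**What to change.** **Protocol 6.3, footnote q of both schedules, and 7.3.1.** State that the mutation blood sample is drawn as close as possible to the last dose of bosutinib and before the first dose of any subsequent anti-leukemia therapy, still within the EOT window. Add that this governs the blood draw only and must not delay that therapy. Require the draw date and the start date of subsequent therapy on the eCRF.

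**SAP 6.1 and 8.2.1.** Keep the percentage based on all samples. Flag each sample drawn after new therapy began, and report the emergent-mutation percentage also for pre-switch samples only. Post-switch samples stay in the main denominator. Each figure has its own weakness (contamination by later therapy in one, selection in the other), so they should be read together.

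**Cost.** Two eCRF dates and one extra table row, with the same tube and the same central laboratory.

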6.4. Long-Term Follow-up Visit

Patients who discontinue treatment with bosutinib prior to the end of the study will enter into the Long-Term Follow-Up period. Patients will be followed for the duration of study in order to assess the survival status of the patient. Details of any subsequent therapy with TKIs or other anti-cancer therapy and response following bosutinib discontinuation will be collected on LTFU patients if available.

Follow-up will be conducted every 3 months from the last dose of bosutinib. Information will be collected via clinical visit or telephone contact

6.5. Patient Withdrawal

Patients may withdraw from the study at any time at their own request, or they may be withdrawn at any time at the discretion of the investigator or sponsor for safety or behavioral reasons, or the inability of the patient to comply with the protocol required schedule of study visits or procedures at a given study site.

Reasons why a patient may discontinue or be withdrawn from the study include, but are not limited to, adverse event patient request, protocol violation, patient noncompliance, and study termination by the sponsor. When a patient discontinues or is withdrawn, the investigator will notify the sponsor.

The treatment completion visit must be performed for all patients who discontinue from receiving further bosutinib administration. Furthermore, follow-up should be performed unless the patient died, voluntarily withdrew consent, or the sponsor terminated the study. All information should be recorded on the appropriate eCRF.

If a patient withdraws from the study, and also withdraws consent for disclosure of future information, no further evaluations should be performed, and no additional data should be collected. The sponsor may retain and continue to use any data collected before such withdrawal of consent.

If a patient does not return for a scheduled visit, every effort should be made to contact the patient. In any circumstance, every effort should be made to document patient outcome, if possible. The investigator should inquire about the reason for withdrawal, request that the patient to return all unused investigational product(s), request the patient to return for a final visit, and follow-up with the patient regarding any unresolved adverse events (AEs).

If a patient is lost to follow-up, or is voluntarily withdrawn from any study participation, every effort must be made to obtain any pertinent follow-up information and/or perform a treatment completion visit.

7. ASSESSMENTS

Every effort should be made to ensure that the protocol required tests and procedures are completed as described. However it is anticipated that from time to time there may be circumstances outside of the control of the investigator, which may make it unfeasible to perform the test. In these cases the investigator will take all steps necessary to ensure the safety and well-being of the patient. When a protocol required test cannot be performed the investigator will document the reason for this and any corrective and preventive actions which he/she has taken to ensure that normal processes are adhered to as soon as possible. The study team will be informed of these incidents in a timely fashion.

7.1. Efficacy Assessments

7.1.1. Efficacy Assessment Methods

Efficacy will be determined by analysis of peripheral blood and physical examination for all patients except those in advanced phase of the disease for whom a bone marrow differential count will be needed. Refer to the [Schedule Of Activities](#) for time points. Assessments will continue per [Schedule Of Activities](#) until treatment completion.

Automated complete blood counts and differential counts (with manual confirmation of abnormalities), physical examination and cytogenetics by FISH will be used to determine response to treatment as outlined in [Appendix 1](#).

Number of Ph⁺ cells will be assessed by fluorescence in situ hybridization (FISH) from peripheral blood (PB) sample. To ensure reliable estimation of cytogenetic response, the cytogenetic assessment must be performed on at least 200 nuclei. PB FISH is not only more sensitive but also less invasive for the patient than conventional bone marrow (BM) cytogenetics.²⁹ Studies have demonstrated the strong correlation between BM and PB FISH as well as BM conventional cytogenetics.³⁰⁻³⁷

However, conventional cytogenetics on BM, requiring at least 20 metaphases, may be performed when loss of cytogenetic response is suspected by PB FISH or at the end of therapy. Loss of cytogenetic response must be confirmed by 2 assessments at least 4 weeks apart.

Hematologic responses must be of at least 4 weeks in duration confirmed by 2 assessments at least 4 weeks apart. Hematologic response will be evaluated by peripheral blood only for patients in chronic phase and by both peripheral blood and bone marrow for patients in advanced phase. Loss of hematologic response must also be confirmed by 2 assessments at least 2 weeks apart.

Molecular response monitoring using reverse transcriptase polymerase chain reaction (RT-PCR) measurement of BCR-ABL fusion transcript levels may be performed on peripheral blood in lieu of monitoring the patient via cytogenetics, once molecular response is achieved, and according to standard of care and current treatment guidelines at Site. This data will be collected in the eCRF.

Physical examination will be used to assess hepatic and spleen involvement.

All tests described above will be performed locally.

